10.5 Study Compliance

The study drugs PLX9486 and PLX3397 will be provided only to eligible patients under the supervision of the investigator or identified sub-investigator(s). The appropriate study personnel will maintain records of study drug receipt and dispensing. Any discrepancy regarding the dose administered and the reason for the discrepancy will be recorded in the eCRF. At each clinic visit, patients will be questioned about their compliance with study drug administration, and their dosing diary should be reviewed.

10.6 Enrollment of Patients

After potential patients have been identified by the site personnel and informed consent has been obtained, the site will inform the Sponsor/Sponsor's representative and a slot will be reserved for the patient. Once all screening assessments are completed, the site personnel will email the Sponsor/Sponsor's representative with the enrollment packet. The Sponsor's medical monitor or designee will review and approve the enrollment (via email typically) and inform the Sponsor's representative that the patient has been approved for enrollment and assign the appropriate dose level. Further information may be found in the study manual.

10.7 Protocol Violations and Deviations

Protocol violations are defined as significant departures from protocol-required processes or procedures that affect patient safety or benefit potential, or confound assessments of safety or clinical activity. A protocol deviation is a departure from the protocol that does not meet the above criteria. Protocol violations or deviations may be grouped into the following categories:

- Enrollment criteria
- Study activities (e.g., missed evaluations or visits, data verification issues)
- Noncompliance with dose or schedule, including dose calculation, administration, interruption, reduction, or delay, or discontinuation criteria
- Investigational product handling, including storage and accountability
- Informed consent and ethical issues

11.0 STUDY ASSESSMENTS

Event schedules are summarized in [Table 1](#) (Part 1), [Table 2](#) [REDACTED] [Table 3](#) (Part 2b), [Table 4](#) [REDACTED] [Table 5](#) [REDACTED] [Table 6](#) (Part 2e), and [Table 7](#) [REDACTED]

All patients must provide written informed consent. During the consent process, the person obtaining consent must inform the patient of all elements of the study. No protocol-specific procedures, including Screening procedures, are to be performed until the patient has signed and dated an institutional review board (IRB)/independent ethics committee (IEC)-approved informed consent form. The study begins with the signing and dating of the informed consent form.

A patient will be considered enrolled in the study once all inclusion and exclusion criteria have been met, and the completed patient enrollment form has been submitted to Plexxikon Inc., signed by the appropriate representative, and returned to the investigative site.

Screening procedures are to be performed within 21 days before Cycle 1 Day 1 of study therapy. Each treatment cycle for Part 1, [REDACTED] 2b, [REDACTED] 2e, and [REDACTED] will be 28 days.

Dose interruptions in the middle of a treatment cycle will not affect the cycle and day count on the schedule of assessments. For example, if study drug is held on Cycle 1 Day 10, the following day should still be called Cycle 1 Day 11, etc. If a dose interruption occurs at the beginning of a new cycle, then the new cycle and day count will begin when study drug is restarted. For example, if study drug is held at the Cycle 2 Day 1 visit, then the day that the patient does resume dosing will be called Cycle 2 Day 1.

The end of the study for each patient is defined as the date of the last dose of PLX9486, PLX3397, or sunitinib (see [Section 10.4](#) for reasons for discontinuation or withdrawal of a patient from the study).

11.1 General Guidelines for Performing Study Assessments

The following procedures, on the days scheduled, should be performed *before* the morning dose of study treatment:

- Predose vital signs.
- Predose 12-lead ECG.
- Predose blood sampling (e.g., clinical laboratory tests, PK, PD, circulating DNA).
Note: All blood sampling should be performed *after* the ECG and assessing vital signs.
- AE assessment.

The following procedures, on the days scheduled, should be performed *after* the morning dose of study treatment:

- Postdose 12-lead ECG.
Note: Unless otherwise stated, the time points for postdose ECGs have a collection window of ± 30 minutes.
- Postdose vital signs.
Note: The time point for assessing postdose vital signs has a window of ± 30 minutes.
- During Cycle 1, the postdose PK sample at Hour 1 has a collection window of ± 10 minutes; subsequent collection time points have a window of ± 30 minutes.
- AE assessment.

11.2 Study Procedures

11.2.1 Electrocardiograms

Patients should rest in the supine or semi recumbent position for at least 5 minutes before each 12-lead ECG recording is started. The ECGs should be reviewed, signed, and dated by a qualified physician (or qualified physician's assistant or nurse practitioner) and any clinically important finding recorded on the appropriate eCRF. The investigator is responsible for providing the interpretation of all ECGs. The results will include heart rate, respiratory rate (RR), PR interval, QRS interval, QT interval, and QTcF interval.

11.2.2 Tissue Biopsy Samples

Archival tissue slides will be collected and stored for subsequent evaluation using a project-specific companion diagnostic assay to be performed at one or more central laboratories.

For Part 2 an optional predose and Cycle 2 Day 1 paired tumor tissue biopsy of a progressive lesion may be obtained in patients with accessible tissue. KIT mutation testing of archival tissue and freshly obtained biopsies will be performed at one or more central laboratories. Data will be tabulated and mutation status correlated with response to treatments.

Tissue specimens from all patients at the Screening visit will be collected and retained for future validation of a KIT mutation assay.

At any time during the study, after informed consent has been obtained, the investigator, at their discretion, may obtain a fresh tumor biopsy from a representative lesion. If a biopsy is obtained, a block, partial block, or at least 10 unstained slides should be sent to the sponsor.

11.2.3 Optional Fresh Tumor Biopsy and Circulating Tumor DNA

This may be taken at any time in per the discretion of the investigator and after informed consent is obtained from the patient. All patients will be required to permit exploratory evaluations of their archival tumor tissue whenever archival tissue is available. If >6 months (approximately) have elapsed since the last biopsy, a repeat biopsy/ies of representative lesions (in the judgment of the investigator) are recommended. Patients with biopsy-accessible tumors in Part 2 will also be asked to consider participation in optional exploratory evaluations of paired biopsies. If a fresh paired biopsy is obtained, the biopsies should be from the same lesion if possible/feasible, and preferably from a non-target lesion.

Circulating tumor DNA (ctDNA) will be collected at baseline, every treatment cycle, and at disease progression.

Further handling/shipping instructions may be found in the study manual. Refer also to [Section 11.2.2](#).

11.2.4

[REDACTED]

[REDACTED]

[REDACTED]

[REDACTED]

11.2.5 Physical Findings

Physical findings will be assessed via a complete physical examination (at protocol-specified visits). All other physical examinations will be disease-specific and symptom-directed. Photography may be included as part of the physical exam for those patients who consent to the procedure.

11.2.6 Redacted Copies of Reports, Scans, or Photographs for the Sponsor

The sponsor may request redacted copies of study procedures such as pathology reports, scans, or photographs obtained during the study as appropriate.

11.2.7 Pharmacology Assessments

11.2.7.1 Pharmacokinetics

During Parts 1 and 2, blood samples will be obtained to determine the PK of PLX9486 as a single agent and also the PK of the combination of PLX9486 and PLX3397 and of PLX9486 and sunitinib. Once the PK of PLX9486 as a single agent is determined in the fasted state, food effect may be explored.

11.2.7.2 Pharmacodynamics

During Parts 1 and 2, blood samples will be obtained for ctDNA and potentially other exploratory PD markers. Tissue samples will be analyzed for KIT mutations per [Section 11.2.2](#).

11.3 Blood Collection

The estimated volume of blood to be collected at each visit for Part 1 and Part 2 of the study are shown in [Table 26](#). The quantities of blood are within accepted limits of 10.5 mL/Kg or 550 mL (whichever is smaller) per NIH and other published guidelines ([DF/HCC 2012](#); [NIHCC 2009](#); [NS LIJ 2013](#)).

Table 26: Potential Blood Sample Volumes Collected in Parts 1 and 2

TEST ▼	STUDY DAY ►	Screening	Blood Sample Volumes (mL)							
			Cycle 1		Cycle 2		Cycle 3+		EOS	
Day -21 to -1	Day 1	Day 2 ±1 d	Day 8 ±2 d	Day 15 ±2 d	Day 22 ±2 d	Day 1 ±7 d	Day 8 ±2 d	Day 15 ±3 d	Day 22 ±2 d	Day 1 ±7 d
Hematology	8	8	8	8	8	8	8	8	8	8
Chemistry	8	8	8	8	8	8	8	8	8	8
Coagulation tests	8	8				8				8
Blood for Biomarker Assessment (PD)		10		10						
Circulating DNA	40	40		40		40		40		40
PK Blood Samples		18	3	18	3	3	3	3	3	15
Total Volume^{a,b}	64	92	19	16	84	19	19	67	16	67
										79

EOS = end-of-study; PD = pharmacodynamic; PK = pharmacokinetic

^a The maximal blood volume drawn per day is about 95 mL. The total blood volume drawn over 8 weeks is approximately 462 mL.^b Totals represent maximum blood volume drawn for any cohort on study. Depending on cohort enrollment and patient duration on study, blood volume may be less than described above for the 8-week period of Cycle 1 and 2.

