5.5.1 Study PLX121-01: Preliminary Results

The study described in this protocol, PLX121-01, is a 2-part Phase 1b/2a trial to assess the safety, PK, PD, and preliminary efficacy of PLX9486 as a single agent and when used in

combination with PLX3397 or sunitinib in patients with advanced solid tumors and in patients with locally advanced, unresectable, or metastatic GIST who have previously been treated with KIT-directed TKI. The phase 1 portion of the study (Part 1) has been completed.

5.5.1.1 Study PLX121-01 Part 1

Twenty-four patients were enrolled among 5 dose-escalation cohorts ranging from 250 mg/day to 1000 mg/day (Table 10). One DLT was observed in the 1000 mg QD cohort (Grade 3 anemia). Table 11 summarizes the Day 1 and Day 15 (steady state) PK results for these cohorts. The data show a modest increase in exposure at steady state between the 250 mg/day dose ($AUC_{0-24}=18,500 \text{ ng}\cdot\text{hr}/\text{mL}$) and the 1000 mg/day dose ($AUC_{0-24}=21,500 \text{ ng}\cdot\text{hr}/\text{mL}$ [QD] and $24,400 \text{ ng}\cdot\text{hr}/\text{mL}$ [BID]). The difference in exposure between the 1000 mg QD dose and the 500 mg BID dose is not statistically significant. Because AUC_{0-24} at 1000 mg QD reaches the target exposure range (AUC_{0-24} of 19,000 to 36,000 $\text{ng}\cdot\text{hr}/\text{mL}$) and because a further increase in dose is not expected to significantly improve AUC, 1000 mg QD was selected as the RP2D for single-agent PLX9486. A single DLT (Grade 3 anemia; 1000 mg QD) was reported among the 24 patients.

Table 10: Study PLX121-01 Part 1 Patient Enrollment and DLT Summary

Part 1 Cohort	PLX9486 Dose Level	Number Enrolled	Number of DLTs (Adverse Events)
1	250 mg QD	3	0
2	350 mg QD	4	0
3	500 mg QD	3	0
4	1000 mg QD	7	1 ^a
5	500 mg BID	7	0

BID = twice daily; DLT = dose-limiting toxicity; QD = once daily

^a DLT: Grade 3 anemia.

Table 11: Study PLX121-01 Part 1 (Dose Escalation) Pharmacokinetic Profile of Single-agent PLX9486 in Patients with Advanced Solid Tumors

Dose		C1D1		C1D15 (Steady State)			Accumulation Ratio
		C _{max} (ng/mL)	AUC _{0-τ} ^a (ng·hr/mL)	C _{max} (ng/mL)	C _{min} (ng/mL)	AUC ₀₋₂₄ (ng·hr/mL)	
250 mg QD (N = 3)	GeoMean	499	9240	869	716	18500	2.0
	CV%	6.92	8.7	38.4	42.5	43.7	
350 mg QD (N = 4)	GeoMean	348	7200	1010	789	21300	3.0
	CV%	15.0	20.7	27.5	27.9	27.7	
500 mg QD (N = 3)	GeoMean	326	5250	714	462	15400	2.9
	CV%	28.5	37.3	64.9	119	65.8	
1000 mg QD (N = 7)	GeoMean	558	11000	1060	722	21500	2.0

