8.1 Inclusion Criteria

Each subject must meet all of the following inclusion criteria to be enrolled in the study:

1. Male or female ≥ 18 years old.
2. **Part 1, Part 2b, [REDACTED] and Part 2e:** Patients with advanced solid tumors who have tumor progression following standard therapy, have treatment-refractory disease, or for whom there is no effective standard of therapy.

3. [REDACTED]

4. [REDACTED]

5. Women of child-bearing potential (WOCBP) must have a negative serum pregnancy test at Screening (\leq 7 days prior to the first dose of Study drug) and must agree to use an effective form of contraception from the time of the negative pregnancy test up to 6 months after the last dose of study drug. Effective forms of contraception include abstinence, hormonal contraceptive in conjunction with a barrier method, or a double-barrier method. Women of non-childbearing potential may be included if they are either surgically sterile or have been postmenopausal for \geq 1 year.

WOCBP are defined as females who have experienced menarche, have not undergone successful surgical sterilization (hysterectomy, bilateral tubal ligation, or bilateral oophorectomy), and are not postmenopausal. All females are considered to be WOCBP except if they have been postmenopausal or surgically sterile for \geq 1 year.

6. Fertile men must agree to use an effective method of birth control during the study and for up to 6 months after the last dose of study drug. Male subjects with partners who are either pregnant or become pregnant during the study drug treatment period must agree to continue to use a condom for 90 days after the last dose of study drug.
7. All associated toxicity from previous or concurrent cancer therapy must be resolved (to \leq Grade 1 or Baseline) prior to study treatment administration.
8. Willing and able to provide written informed consent prior to any study related procedures and to comply with all study requirements.
9. Eastern Cooperative Oncology Group (ECOG) Performance Status 0–2.
10. Life expectancy \geq 3 months.
11. Adequate hematologic, hepatic, and renal function:
 - a. Absolute Neutrophil Count (ANC) \geq 1.5 \times 10⁹/L
 - b. Hemoglobin $>$ 8 g/dL
 - c. Platelet count \geq 100 \times 10⁹/L
 - d. AST and ALT \leq upper limit of normal (ULN)

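### Section 11.3 claims without condition that blood draws stay within 10.5 mL/kg, but the protocol's own 462 mL maximum meets that limit only from 44 kg, and no visible rule covers lighter patients

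*Protocol*

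**What the plan says.** Section 11.3 makes a compliance statement that applies to every patient: "The quantities of blood are within accepted limits of 10.5 mL/Kg or 550 mL (whichever is smaller) per NIH and other published guidelines". It names no period over which the limit runs, and it does not say whether safety laboratory blood counts or only research blood.

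The footnotes to Table 26 give the volumes. Footnote a: "The total blood volume drawn over 8 weeks is approximately 462 mL". Footnote b qualifies this in two ways: "Totals represent maximum blood volume drawn for any cohort on study", and, depending on cohort and time on study, "blood volume may be less than described above for the 8-week period of Cycle 1 and 2". The table adds safety tests (hematology, chemistry, coagulation) to research samples (PD biomarker, circulating DNA, PK).

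The readable inclusion and exclusion criteria (sections 8.1 and 8.2) contain no minimum body weight. Inclusion criteria 3 and 4 and exclusion criterion 3 are redacted and cannot be checked. Section 11.3 has no provision to reduce sampling by weight.

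**The concern.** The limit has two arms and the smaller one binds. For a light adult that is the per-kilogram arm, and it falls with weight while the scheduled volume does not. A fixed volume and a limit proportional to weight can agree for everyone only if there is a weight floor or a volume rule, and neither is visible here.

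A site or ethics committee that reads 11.3 is told the limit is met for all patients. If it is not, the protocol gives staff no signal that a light patient needs separate handling and no statement of which draws may be omitted. As context, entry is allowed with hemoglobin just above 8 g/dL (section 8.1), and the one DLT reported in Part 1 was anemia: "A single DLT (Grade 3 anemia; 1000 mg QD) was reported among the 24 patients". That is a reason to have the statement right. It is not evidence that sampling has harmed anyone.

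**Working it through.** **Inputs, all from section 11.3.** Limit at weight w: L(w) = min(10.5 × w, 550) mL. Stated maximum volume over 8 weeks: V = 462 mL. Table 26 total row as extracted: 64, 92, 19, 16, 84, 19, 19, 67, 16, 67, 79. The first is Screening and the last is end of study (EOS). There are eleven totals for about twelve visit columns, so the extraction appears to have lost one, and sums of this row are approximate.

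**Reproducing 462 mL.**
- Screening through the last visit before EOS: 64 + 92 + 19 + 16 + 84 + 19 + 19 + 67 + 16 + 67 = 463 mL, 1 mL from the stated figure.
- The same run without Screening: 463 − 64 = 399 mL.
- No other consecutive run of visits comes within 14 mL of 462. An exact 462 also arises from dropping Screening and one 16 mL visit and adding EOS (542 − 64 − 16), but that selection corresponds to no stated window.

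So the stated figure most plausibly includes Screening, although footnote b describes the period as Cycles 1 and 2.

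**Weight at which the limit is met.** The threshold is V/10.5. The 550 mL cap takes over at 550/10.5 = 52.4 kg, and 462 mL does not exceed it.

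| Weight | Limit (mL) | 462 mL against limit |
|---|---|---|
| 35 kg | 367.5 | 94.5 over |
| 40 kg | 420 | 42 over (10%) |
| 42 kg | 441 | 21 over |
| 44 kg | 462 | exactly met |
| 50 kg | 525 | 63 under |

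**How the threshold moves with what is counted.**

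| Volume counted | mL | Met from (kg) |
|---|---|---|
| Stated maximum | 462 | 44.0 |
| Extracted totals, no Screening | 399 | 38.0 |
| With Screening, last 67 mL visit treated as Cycle 3 | 463 − 67 = 396 | 37.7 |
| Neither | 399 − 67 = 332 | 31.6 |
| Research rows only (an assumed split) | 234 to 274 | 22.3 to 26.1 |
| Stated maximum plus escalation PK | 462 + 36 = 498 | 47.4 |

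For the last row, the flow charts ask for six PK samples on the first day of within-patient escalation and six more on Day 15 after it. Table 26 shows 18 mL for a six-sample day, or 3 mL each, so 12 × 3 = 36 mL. If escalation starts on Cycle 2 Day 1 and the scheduled predose samples on Days 1 and 15 are already counted, the addition is 30 mL and the threshold is 492/10.5 = 46.9 kg.

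**The case against.** The strongest reply is that 44 kg is not a firm number. Footnote b ties the total to Cycles 1 and 2, and Screening lies before them. Without Screening the extracted totals give 399 mL, and a 40 kg patient with a limit of 420 mL is then inside it. The figure of 462 mL, or its 8-week label, may be what needs correcting. This stands, and it is why the fix starts with the window and the total. It does not rescue the sentence, because 462 mL is the only cumulative volume the protocol offers, and every reading leaves some weight below which an unconditional claim fails.

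Second, 462 mL is a ceiling. Footnote b says so, and the flow charts waive repeat Cycle 1 Day 1 safety laboratory tests if Screening was within 2 days: 24 mL in Table 26, giving 438/10.5 = 41.7 kg. This also stands, but a statement of compliance has to hold for the maximum schedule.

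Third, if only research blood counts, the threshold falls to about 22 to 26 kg and the practical problem largely disappears. The protocol makes no such split, and the cited guidelines are not available here to settle it.

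A reader might go further and infer three things that the documents do not support:
- **A safety breach.** The number of patients under 44 kg is not given, the total mixes safety and research blood, and redacted criteria might contain a weight floor.
- **Sampling that produces false DLTs.** This needs an assumed blood volume per kilogram and a very light patient entering near 8 g/dL. Section 9.3 also requires a DLT to be judged possibly or probably drug-related and lists Grade 4 anemia as the hematologic criterion, although a Grade 3 anemia was in fact counted.
- **A redundant circulating DNA draw at Screening or Cycle 1 Day 1.** Section 11.2.3 says "Circulating tumor DNA (ctDNA) will be collected at baseline, every treatment cycle, and at disease progression", so the Day 1 draw can be the per-cycle sample, and section 11.4 gives circulating DNA an eligibility use.

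**Conclusion.** The point holds as an internal contradiction in section 11.3. On the protocol's own figures, the unconditional statement is true only for patients of 44.0 kg or more who follow the maximum schedule. At 40 kg the excess is 42 mL (10%), and at 35 kg it is 94.5 mL.

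This rests on applying the limit to the 8-week total and on counting all the blood in that total. Leaving Screening out moves the threshold to about 38 kg, and escalation PK sampling can move it up to 47.4 kg. It also rests on the readable eligibility criteria, since three are redacted. How many patients are affected is unknown and may be few. The anemia DLT and the anemia SAE are context only. What is established is that a stated safety limit is asserted for everyone without the window, the weight condition or the sampling rule needed to make it true.

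**What to change.** In section 11.3 and Table 26:

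1. State the period to which the limit applies and which blood counts toward it (all blood, or research blood only).
2. Reconcile the 462 mL total with that period, saying whether Screening and the first Cycle 3 visit are included, and add a line for PK samples taken after within-patient escalation.
3. Make the compliance sentence conditional on weight: met from 44 kg if 462 mL stands, otherwise from the reconciled total divided by 10.5.
4. Add that, where a patient's scheduled volume would exceed 10.5 mL/kg, exploratory draws (circulating DNA, PD biomarker) not needed for eligibility or safety are reduced or skipped until the limit is met.

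A rule tied to the limit works better than deleting fixed samples. Dropping two 40 mL circulating DNA draws for everyone leaves 462 − 80 = 382 mL, which is still over the limit below 382/10.5 = 36.4 kg.

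The cost is wording in section 11.3, Table 26 and a flow-chart footnote, plus a few exploratory samples lost in very light patients. No primary or secondary endpoint depends on those samples.

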11.4 Biomarker Samples and Pharmacogenomics

Baseline subject blood samples (serum, plasma, whole blood) will be obtained for pharmacodynamic and biomarker assessments. These may be repeated at subsequent time points throughout the study. In addition, subjects will be asked to submit archival tumor samples, and may be asked to have subsequent tumor biopsies while on the study. These tumor samples may also be used for pharmacodynamic and biomarker assessments. While some of the assessments are prospectively described in the protocol, new assessment methods may emerge during the study or after it has concluded. Hence some samples may be stored and analyzed at a later date as newer technologies emerge.

Pharmacodynamic and other biomarker samples may be used to identify prognostic or predictive biomarkers. In addition, they may be used to improve the understanding of the biology of the disease under study, the metabolism of the drug, to help identify subjects who may be more or less likely to benefit from the drug, or who may be at risk for potential toxicity from the drug.

Analyses to be done on the samples (blood and tumor) for this study may include, but are not limited to:

- Genetic analyses of tumor tissues for mutations of KIT
- Circulating tumor DNA in blood
- Circulating tumor DNA and tumor biopsy-derived DNA (if available) will be analyzed for KIT exon mutations, PDGF-R, SDH, and NF-1 mutations to determine eligibility for the planned extension cohort.
- Genomic analysis and expression arrays may also be performed for exploratory purposes

The science of biomarkers and assays is always evolving and therefore a definitive list of biomarkers remains to be determined and may include additional markers suggested by preclinical/clinical research or referenced in the literature or other scientific conferences as the science and technology evolve.

Stored samples will only have the patient study number as an identifier, and will not have any patient identifying information such as name, birthdate, etc. Samples will be stored for 3 years after the end of the study, or per local guidelines, and then they will be destroyed.

As part of this study, blood samples will be collected for pharmacogenomics analysis. Where required by local regulations, participation in pharmacogenomic sample collection is optional and will be addressed in a separate Pharmacogenomics ICF at screening. In these regions, subjects who choose not to provide a sample for pharmacogenetic analysis may still participate in the study.

For subjects who participate in pharmacogenetic testing, a blood sample should be collected at the screening visit(s) or as indicated in the schedule of assessments. This sample may be analyzed only for genes suspected to contribute to the safety and efficacy of the study medications. The analysis may also include a comprehensive evaluation of genetic information,

with a particular focus on specific genetic changes considered to potentially predict responsiveness or resistance to treatment.

Results may also provide information on how individuals metabolize and react to the study drug or help to identify subjects who are more or less likely to benefit from the study drugs. The information may be useful to increase the knowledge of differences among individuals in the way they metabolize the study drug, as well as helping in the development of new drugs or improvement of existing drugs.

Because emerging information regarding the safety and efficacy of study medications may become available in the future, pharmacogenomic samples may also be banked for possible future research. In all regions, pharmacogenomic sample banking is optional and will be addressed in a separate Pharmacogenomics ICF at screening. Samples will be retained until the DNA has been exhausted or until the sponsor instructs the genotyping contractor to destroy the sample (in accordance with laboratory procedures). During the period of storage, the DNA sample will not be immortalized or sold to anyone. Subjects will have the right to withdraw consent and have their sample destroyed at any time.

The samples will be shipped to a central laboratory for forwarding to analysis laboratory(ies), which has been contracted by the sponsor to process these samples.

In order to ensure subject confidentiality, sample tubes will be identified only by a barcode label. This barcode will be linked to the subject's SID number. Samples will be stored for 3 years after the end of the study, or per local guidelines, and then they will be destroyed.

Sample collection, preparation, handling, storage, and shipping instructions are in the Laboratory Manual.

